8.4 Demographic and Other Baseline Characteristics

All demographic and baseline summaries will be displayed for the mITT Population, Safety Population and PP Population.

Gender, race, ethnicity, and female childbearing potential will be summarized using counts and percentages. Age, height, and weight will be summarized with descriptive statistics (number of patients, mean, standard deviation, median, minimum, and maximum). Age group (≥ 18 to < 65 years, ≥ 65 to < 75 years, and ≥ 75 years) will be summarized using counts and percentages.

The number and percentage of patients with abnormal physical examination findings at screening will be summarized. The number and percentage of patients with medical history events will be summarized. Vital signs collected at baseline (blood pressure, heart rate, respiratory rate, and body temperature) will be summarized with descriptive statistics (number of patients, mean, standard deviation, median, minimum, and maximum).

Baseline characteristics of HCC will be summarized using counts and percentages as follows:

- Child-Pugh class (A [A5 or A6] or B)
- BCLC stage (B or C)
- HCC etiology (alcoholism, hepatitis B, hepatitis C, afloxatin-contaminated food, non-alcoholic fatty liver disease, other (including unknown)); note that patients with more than one etiology are recorded under “other” so two summaries will be provided:

- based on data directly from these etiology pre-specified categories on CRF
- patients with more than one etiology recorded under “other” will be summarized once under each corresponding category (for example, “alcoholism and hepatitis B” entered in the “other, specify” free text field will be summarized under the pre-defined categories of alcoholism and hepatitis B separately); only patients with etiologies that do not fall into the pre-defined categories will be summarized under “other” (including patients with unknown etiology)
- HCC etiology (alcoholism, non-alcoholism) as defined in Section 7.2
- Extrahepatic disease at baseline (yes or no)
- Duration from date of initial diagnosis of HCC to randomization (<6 months, \geq 6 months; <12 months, \geq 12 months)
- Tumor replacement at baseline separately by investigator assessment and by blinded central review (<20% or \geq 20%)
- Prior oncologic treatment for HCC (yes or no, as well as summarizing separately for liver directed therapy, prior resection, or systemic treatment)
- Hepatoma Arterial-Embolization Prognostic (HAP) score at baseline (1, 2, 3, or 4)
 - Patients are assigned one point for each of the following:
 - Bilirubin at baseline \geq 1 mg/dL
 - Albumin at baseline <3.6 g/dL
 - AFP at baseline >400 ng/mL
 - Longest diameter of largest target lesion at baseline according to RECIST 1.1 by investigator assessment >7 cm
 - Bilirubin at baseline (<1 mg/dL or \geq 1 mg/dL)
 - Albumin at baseline (<3.6 g/dL or \geq 3.6 g/dL)
 - ALBI score at baseline (1, 2 or 3)
 - AFP at baseline (<200 ng/mL or \geq 200 ng/mL; <400 ng/mL or \geq 400 ng/mL)
 - Maximum lesion size at baseline, defined as the longest diameter of largest target lesion at baseline according to RECIST 1.1 by investigator assessment (<7 cm or \geq 7 cm)
 - HCC related stratification factors
 - HCC status (unilobar vs. bilobar disease)
 - ECOG performance status (0 vs 1) at baseline
 - Presence or absence of branch PVT at baseline
- Note: stratification factors according to the master file, with any incorrect values at randomization replaced with the corrected value from the eCRF, will be used. Patients randomized after the stratification change to replace HCC status with Region will have their HCC status assigned based on the eCRF collected HCC status.
- Baseline number of lesions (<3 lesions, 3-5 lesions, 6-10 lesions, >10 lesions) by blinded central review

The time from diagnosis of HCC to randomization and tumor replacement at baseline (separately by investigator assessment and by blinded central review) will also be summarized descriptively.

Baseline tumor replacement (%) will be summarized with descriptive statistics (n, mean, SD, median, min, and max) by treatment group, and also as the number and percentage of patients with tumor replacement <20% and $\geq 20\%$.

Pregnancy test results will be summarized by number and percentage.

8.5 Prior and Concomitant Therapy

The WHO DE March 2011 dictionary will be used to classify medications by preferred term and WHO Anatomical Therapeutic Chemical (ATC) classification of ingredients.

The following applies to all data collected on the prior and concomitant eCRF page and will be reported by each category separately.

Where a medication start date is missing, this medication will be assumed to be concomitant for reporting purposes, unless the end date is prior to the date of randomization. Partial dates will be imputed as detailed in Section 6.2.1.3.

Frequency counts and percentages will be provided to summarize the use of prior and concomitant medications by WHO ATC classification of ingredients and by preferred term.

8.5.1 Prior Medication

A prior medication is defined as any medication stopped prior to the date of randomization.

The number and percentage of patients who had at least one prior medication will be tabulated as well as the number and percentage of patients with each medication. Patients will only be counted once for each medication.

8.5.2 Prior Therapy for HCC

Prior HCC treatment type and treatment will be summarized from the treatment type and treatment recorded on the Medical History of HCC eCRF page.

8.5.3 Concomitant Medication

A concomitant medication is defined as any medication given prior to the patient being randomized and continuing after randomization, or any medication that is initiated on or after randomization. Medications are considered concomitant through to the end of the study.

The number and percentage of patients who had at least one concomitant medication will be tabulated as well as the number and percentage of patients with each medication. Patients will only be counted once for each medication.

8.6 Analysis of Efficacy Parameters

8.6.1 Analysis of Primary Efficacy Variable

The primary efficacy analysis is of OS. OS rates will be derived from the Kaplan-Meier estimates for each treatment group; 6, 12, 18 and 24 month OS rates will be presented, together with 95% confidence intervals (CIs). Quartiles will be presented and 95% CIs will also be calculated on the quartiles for each treatment group. A log-rank (two-sided) test, converted to a z-score, will be used to compare OS between the two treatment groups at an overall two-sided alpha level of 0.05. The two-sided alpha level of 0.05 will be adjusted over the 2 planned interim analyses and final analysis (as described in Sections 7.4 and 7.5). The HR and corresponding two-sided 95% CI for the treatment effect will be computed from a Cox proportional hazards model. Plots of the Kaplan-Meier curves will be provided for each treatment group. This analysis will be performed on the mITT population (primary analysis) and PP population (secondary analysis).

The assumption of proportional hazards used to compute the HR for OS will be assessed. Firstly, a plot of log[-log (estimated probability of event-free survival)] versus log(time) will be examined, with nonparallel curves for the 2 treatment groups indicating non-proportional hazards. Also, a time-dependent covariate Cox regression model (i.e. adding a treatment group by time interaction) will be fitted and if the time-dependent covariate has two-sided p-value <0.15 piecewise HRs over distinct time periods will be calculated.

For each patient that has not known to have died, OS will be censored at the time of last contact date known to be alive.

Note that any patient who is still on the study and has not withdrawn or died at the data cut-off (DCO) date for the final analysis will have an additional survival contact on the day of DCO or within 2 weeks of DCO date, with Patient Contact/Overall Survival log and/or Confirmation of Death eCRF page to be completed accordingly. If patients are confirmed to be alive or if the death date is after the DCO date these patients will be censored at the date of DCO.

All patients should be followed for OS, however, if a patient has not known to have died and not been followed for OS for any reason (i.e. no contact date known alive on Patient Contact/Overall Survival log eCRF page), censoring date will be defined as the latest among the following dates recorded on the eCRF:

- Adverse event start and end dates

[figure not shown]
- Dates of collection for laboratory tests (hematology, coagulation, chemistry)
- Date of collection for AFP
- ECOG assessment date
- FACT-Hep assessment date
- Child Pugh Score assessment date
- TheraSphere administration date
- Sorafenib administration start and stop dates
- Date of imaging on Determination of Response eCRF page
- Date of curative treatment on Resection / HCC Stage Migration eCRF page
- Best available care start and end dates on Best Available Care - Post Treatment Discontinuation - Medication eCRF page
- Procedure start and stop dates on Additional Procedures eCRF page
- Date of study exit on Study Exit eCRF page

Sensitivity analysis will be performed to address the poolability of data (See Section 8.6.5).

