Statistical Plan and Sample Size Calculation	
This study is an adaptive trial using a group sequential design with overall survival (OS) as the primary efficacy endpoint.
 
A modified Intention To Treat (mITT) Population will be used to analyze all efficacy endpoints. This population is defined as randomized patients who met the study eligibility criteria at randomization.
 
The study is designed to detect a 3.5 month increase in median OS time, from 10.7 months in the sorafenib arm to 14.2 months in the TheraSphere arm (ie, hazard ratio = 0.754), using a log rank test. Due to uncertainty in the expected treatment effect, a sample size re-estimation is planned, which would allow the sample size to increase in order to detect a 3.0 month increase in median OS time, from 10.7 months in the sorafenib arm to 13.7 months in the TheraSphere arm (ie, hazard ratio = 0.781).
 
A maximum of 417 deaths will yield 80% power to detect the target difference in median OS (ie, hazard ratio = 0.754) with a two-sided alpha of 0.05 using a group sequential design with 2 interim analyses. It is estimated that a maximum of 520 patients will need to be recruited over 60 months, with an 18 month additional follow-up period. This includes an adjustment to take account of an assumed 5% of patients who will be lost to follow-up and for whom a date of death is not recorded, and an assumed additional 5% of patients who will be erroneously randomized because they did not meet the eligibility criteria at randomization.
 
[REDACTED]
 
[REDACTED]
 
[REDACTED]
 
Analysis of primary endpoint
 
OS will be compared between treatment arms using a log-rank test. The hazard ratio and corresponding two-sided 95% confidence interval (CI) for the treatment effect will be computed. Kaplan-Meier curves will also be produced.
 
Interim analyses of primary endpoint: The first interim analysis is planned at approximately, but no less than, 188 deaths, with a two-sided p-value ≤ 0.0151

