7.4 Interim Analyses and Data Monitoring

An IDMC will be established to oversee the conduct of the study. The IDMC will meet periodically during the study to review enrollment, protocol deviations and safety events for the study. In addition, the IDMC will conduct and review the interim efficacy results and will make formal recommendations to the study Sponsor at the time of the interim analysis and during the conduct of the study.

After the first 20 patients in the treatment group have received TheraSphere followed by at least 2 weeks of sorafenib therapy, a feasibility safety assessment will be conducted. The IDMC will review the safety results of both the control and treatment groups in an unblinded fashion. The IDMC will take into consideration the established safety profiles of TheraSphere and sorafenib as described in the package inserts for each product as well as the published literature. The expected high rates of AEs events and death that are associated with disease progression in patients with HCC will be considered.

A consideration for stopping further enrollment to the trial may be made if there is a pattern of serious toxicity clearly related to the sequential administration of TS followed by sorafenib. Such a toxicity pattern must be clearly different from, or more severe than, what might be expected from independent administration of the products. The potential adverse impact of any such pattern of toxicity on the survival or well being of the patient should be considered in the context of the safety and outcome expectations of patients with advanced HCC.

This study uses an adaptive group sequential design with two interim analyses and one final analysis. The efficacy stopping boundaries are based on the rho family error spending function with the parameter value rho=1.5. The first interim analysis is planned at approximately, but no less than, 188 deaths, with a two-sided p-value ≤ 0.0151 allowing the study to be stopped early for efficacy. A second interim analysis is planned at approximately, but no less than, 250 deaths, with a two-sided p-value ≤ 0.0151 allowing the study to be stopped early for efficacy. If the interim analyses do not occur at exactly 188 or 250 deaths, the corresponding efficacy boundaries were to be calculated using the rho family spending function with rho=1.5.

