The boundary for the final analysis will be adjusted based on the first and second interim analyses and the actual number of deaths at the final analysis. The actual number of deaths for the first and second interim analyses were 205 and 257, respectively. However, at the first interim analysis, the efficacy boundary was inadvertently not recalculated based on the actual number of 205 deaths, and instead the p-value scale boundary stated in the SAP, based on the planned number of 188 deaths, was used. The p-value scale boundary at the second interim analysis was based on the planned number of 188 deaths at the first interim analysis, the actual number of 257 deaths at the second interim analysis and the planned final number of 417 deaths. Therefore, for the final analysis, the efficacy boundary (i.e., α_f) will be calculated using the rho family spending function with $\rho=1.5$, based on the planned number of 188 deaths at the first interim analysis, the actual number of 257 deaths at the second interim analysis and actual number of deaths at the final analysis. This will result in a more conservative efficacy boundary than the one using actual numbers of deaths for all scenarios for the actual number of deaths at the final analysis, as shown in Table 8. The efficacy boundary α_f will be fixed and documented prior to database hard lock for the final analysis. A two-sided p-value $\leq \alpha_f$ will be required to declare a statistically significant improvement in OS at the final analysis.

Table 8 Scenarios of Efficacy Boundary at Final Analysis

Actual Number of Deaths at Final Analysis	Two-Sided P-value Scale Efficacy Boundary at Final Analysis	
Based on 188 Planned Deaths at IA1, 257 Actual Deaths at IA2 and Actual Number of Deaths at Final Analysis	Based on 205 Actual Deaths at IA1, 257 Actual Deaths at IA2 and Actual Number of Deaths at Final Analysis	

Actual Number of Deaths at Final Analysis	Two-Sided P-value Scale Efficacy Boundary at Final Analysis	
	Based on 188 Planned Deaths at IA1, 257 Actual Deaths at IA2 and Actual Number of Deaths at Final Analysis	Based on 205 Actual Deaths at IA1, 257 Actual Deaths at IA2 and Actual Number of Deaths at Final Analysis
406	0.0354	0.0355
407	0.0354	0.0355
408	0.0355	0.0356
409	0.0355	0.0356
410	0.0356	0.0357
411	0.0356	0.0357
412	0.0356	0.0358
413	0.0357	0.0358
414	0.0357	0.0358
415	0.0358	0.0359
416	0.0358	0.0359
417	0.0358	0.0360

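### The only planned interval for the primary OS hazard ratio is an unadjusted 95% CI, while the final test needs p at or below about 0.0354 to 0.0358, so the interval can exclude 1 when the test fails.

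*SAP*

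**What the plan says.** SAP 8.6.1 sets the log-rank test for OS at an overall two-sided 0.05 and says that "The two-sided alpha level of 0.05 will be adjusted over the 2 planned interim analyses and final analysis". The next sentence reads: "The HR and corresponding two-sided 95% CI for the treatment effect will be computed from a Cox proportional hazards model". The protocol synopsis agrees: "The hazard ratio and corresponding two-sided 95% confidence interval (CI) for the treatment effect will be computed".

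SAP 7.4 gives the design behind the adjustment: "The efficacy stopping boundaries are based on the rho family error spending function with the parameter value rho=1.5". It also records that "The actual number of deaths for the first and second interim analyses were 205 and 257, respectively". At the final analysis, a two-sided p-value no larger than alpha_f "will be required to declare a statistically significant improvement in OS at the final analysis". Table 8 lists alpha_f, on the basis the SAP adopts, from 0.0354 at 406 deaths to 0.0358 at 417. The value is to be fixed and documented before database hard lock.

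Under SAP 8.6.2 the secondary endpoints are tested in order only if the primary comparison is significant. Otherwise they are reported as exploratory.

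The text provided specifies no repeated, stagewise or (1 - alpha_f) interval for OS, and does not label the 95% CI as nominal or descriptive.

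**The concern.** Readers usually take a primary test and its corresponding interval as two views of one result: the interval excludes the null value when the test is significant. Here the test runs at alpha_f and the interval at 0.05. For any final p-value between alpha_f and 0.05, the report would show an OS hazard ratio with an interval wholly below 1, a failed primary test, and secondary endpoints reduced to exploratory. The plan has no wording to reconcile these. The same 95% interval would also appear as the overall result on the subgroup forest plots (SAP 8.6.4).

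What is at stake is how a near-miss is presented in an open-label trial whose data, according to protocol section 13.6, support a premarket approval application. Both interim analyses have passed and the sample size was not increased (SAP 7.4), so the final analysis is the one that matters now.

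**Working it through.** **1. Inputs.** Spending function, interim and final death counts, and the Table 8 boundaries are from SAP 7.4. Design hazard ratios of 0.754 and 0.781 are from SAP 4.4, and 1:1 allocation from SAP 4.2. Approximation: SE(log HR) = 2/sqrt(deaths).

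**2. Reproducing the plan's boundaries.** One-sided spending is 0.025 × t^1.5.
- First look, where "The first interim analysis is planned at approximately, but no less than, 188 deaths": t = 188/417 = 0.451, spend = 0.00757, two-sided p = 0.0151, as stated.
- Second look, where "A second interim analysis is planned at approximately, but no less than, 250 deaths": numerical integration over 188, 250 and 417 deaths gives 0.0151, and 0.0363 at the final look (z = 2.093). Both match the plan.
- On the basis adopted for the final analysis, 188, 257 and 417 deaths give 0.0358. Looks at 188, 257 and 406, with information fractions on 406, give 0.0354. Both match Table 8. Keeping interim spending on the 417 scale would give about 0.0362 at 406 deaths, still well below 0.05.

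**3. Hazard ratio limits.** Limit = exp(-z × SE), with z = 1.960 for the 95% CI.

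| Final deaths | SE | z at alpha_f | HR for significance | HR at which 95% CI excludes 1 |
|---|---|---|---|---|
| 406 | 0.0993 | 2.104 | ≤ 0.812 | ≤ 0.823 |
| 417 | 0.0979 | 2.099 | ≤ 0.814 | ≤ 0.825 |

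The gap is about 0.011 on the HR scale.

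**4. Example at p = 0.04.**
- 406 deaths: HR 0.816, 95% CI 0.671 to 0.991, but 96.46% CI 0.662 to 1.005.
- 417 deaths: HR 0.818, 95% CI 0.675 to 0.991, but 96.42% CI 0.666 to 1.004.

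In both cases the test fails while the planned interval excludes 1.

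**5. Chance of ending in the gap.** This is the probability of crossing neither interim boundary (205 and 257 deaths) and finishing with z between 1.960 and the final critical value, by numerical integration and by simulation.
- HR 0.754: 3.3 to 3.6%.
- HR 0.781: 4.2 to 4.5%.
- HR 1: about 0.6%, in the direction of benefit.

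The ranges cover the two methods, 406 and 417 deaths, and the alternative boundary at 406.

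Given that the final look is reached, the chance is higher. SAP Appendix 5 gives early efficacy stopping of 45.3% at HR 0.754 (Table 2a) and 34.8% at HR 0.781 (Table 3a) under the planned looks. Then 3.3 to 3.6% divided by 0.547 is 6.0 to 6.6%, and 4.2 to 4.5% divided by 0.652 is 6.4 to 6.9%. Simulation with the actual look times gives 6.4 to 6.8% and 6.7 to 7.1%.

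**6. Coverage of the plain 95% CI at the stopping look (simulation).** It is about 95% at HR 0.754 to 0.82. At HR 1 it is about 94% (94.5% if only stopping for benefit is counted). Among trials that reach the final look it is 95.3 to 96.6%.

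**The case against.** The strongest reply is that the interval has no role in the decision. Success is a log-rank p-value against alpha_f, and the secondary hierarchy opens on that result alone. No text lets the confidence interval declare success, and any report under this plan must show the p-value against its boundary. The 95% level is also the SAP's convention for survival rates, quartiles, secondary hazard ratios and subgroups. All of this stands.

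A reader might go further and infer that the interval is too narrow, or that the mismatch inflates type I error. The documents do not support either reading. The error rate is carried by the test, which is properly adjusted. As an effect estimate the 95% CI keeps close to its nominal coverage (step 6). Boundary-matched intervals used at every look would cover about 95.8 to 97.5%, which is conservative.

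A reader might also size the risk with a fixed-sample formula, which gives about 4% at HR 0.754 and 5% at HR 0.781. That ignores trials that would have stopped early, and it does not answer the conditional question either.

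Finally, matching the levels does not guarantee agreement. The test is log-rank and the interval comes from a Cox model, with discrete handling of ties (SAP Appendix 2), so the two can differ slightly near the boundary at any level.

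What survives is narrower: the only interval planned for the primary endpoint does not correspond to its test, and nothing in the plan says so.

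**Conclusion.** The point holds as a mismatch between interval and test level, and it is a low-cost improvement. For final p-values from about 0.0354 to 0.0358 up to 0.05, the 95% CI excludes 1 while OS fails. The window is about 0.011 wide in observed HR. The chance of ending in it is about 3 to 5% overall at the design hazard ratios, and about 6 to 7% once the final look is reached.

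It should not be read as a flaw in error control, power or the success rule.

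The sizes rest on the normal approximation with SE = 2/sqrt(deaths), proportional hazards, and a final count between 406 and 417 deaths.

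**What to change.** In SAP 8.6.1, add a (1 - alpha_f) confidence interval for the OS hazard ratio as the interval that accompanies the primary test. Its level would be 96.46% at 406 deaths and 96.42% at 417, and should be recorded in the same step that fixes alpha_f before hard lock. State that the 95% CI is nominal and is not used to judge success, and carry that label to the forest plots.

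The cost is one more line of output and no new data or assumptions. The added interval is about 7% wider on the log scale (2.104/1.960 = 1.073; 2.099/1.960 = 1.071). It is somewhat conservative as an estimate and is not a full sequential correction. Slight disagreement between the Cox interval and the log-rank test at the boundary remains possible, and one sentence should say that the log-rank result prevails.

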9.2.20 STUDY COMPLETION

Patients complete the trial upon reaching the primary efficacy endpoint of death. A patient may also decide he/she no longer wishes to participate in the trial. In accordance with the Declaration of Helsinki, and applicable state and federal regulations, a trial subject has the right to withdraw from the study at any time and for any reason. Every effort should be made to have patients complete the study within the provisions of informed consent. However, the participation of the patient may be discontinued at any time during the study when, in the judgment of the investigator, sponsor or subject, it is appropriate.

The reasons for study completion include:

- Death of the patient
- Patient's desire for any reason to withdraw consent
- Administrative reasons
- It is considered necessary by the investigator or sponsor, for any reason

Lost to follow-up is not an adequate reason for withdrawal. Patients should be encouraged to attend study visits until completion of the study or until a decision is taken to withdraw for one of the above-noted reasons.

If intolerance to the study treatment, the patient should be under medical supervision as long as deemed appropriate by the treating physician. Similarly, if study treatment is discontinued due to an AE, the event will be followed until it resolves to the Investigator's satisfaction or is considered stable. The details and reasons for discontinuation must be carefully and completely documented. In either situation, the patient must be followed-up for survival until one of the reasons for study completion is met.

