10.2.2 TRIAL ENDPOINTS

10.2.2.1 PRIMARY EFFICACY ENDPOINT

The primary study endpoint is OS which will be calculated as the interval between the randomization date and the date of death for any cause, with censoring at the date of last contact for patients alive at last contact.

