6.2.1.3 Partial Dates

Partial dates with day or day and month missing will be imputed as follows:

- The missing day of onset of an adverse event (AE) will conservatively be set to the earlier of:
 - First day of the month of the AE start month, if the month of the start date of sorafenib and the date of first angiogram (whichever occurs first) is not the same as the AE start month,
 - One day after the start date of sorafenib and the date of first angiogram (whichever occurs first), if the month of the start date of sorafenib and the date of first angiogram (whichever occurs first) is the same as the AE start month.
- The missing day of resolution of an AE will be set to the last day of the month of the AE end month.
- For other variables, including date of tumor response, and progression, partial dates that need to be imputed will use the 15th of the month to replace the missing day.
- A missing day of death will be replaced by the 15th of the month if there are no other assessments after the 15th of the month for that patient. Otherwise the last day of the month will be used to replace the missing day of death.
- If the onset date of an AE is missing both day and month, it will be set to:
 - January 1 of the year of AE start year, if the year of the start date of sorafenib and the date of first angiogram (whichever occurs first) is not the same as the AE start year,
 - One day after the start date of sorafenib and the date of first angiogram (whichever occurs first), if the year of the start date of sorafenib and the date of first angiogram (whichever occurs first) is the same as the AE start year.
- If the resolution date of an AE is missing both day and month, it will be set to December 31 of the AE end year.
- For the date of initial diagnosis of HCC, a missing day will be set to the first day of the month, and a missing day and month will be set to January 1 of the year.
- For the start date of medications recorded on the “Prior and Concurrent Medications” electronic case report form (eCRF) page, a missing day will be set to the first day of the month, and a missing day and month will be set to January 1 of the year. If month/year of the start date (if only missing day) or year of the start date (if missing month/day) is the same as the month/year or year of the randomization date, respectively, the start date will be set to one day after the randomization date.

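### For patients with no known-alive date on the survival log, the OS fallback rule can censor at a study-exit date on which nobody confirmed the patient was alive

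*SAP*

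**What the plan says.** Protocol 10.2.2.1 defines OS from randomization to death, "with censoring at the date of last contact for patients alive at last contact". SAP 8.6.1 opens with the same principle: "OS will be censored at the time of last contact date known to be alive".

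The SAP then adds a fallback. It applies "if a patient has not known to have died and not been followed for OS for any reason", which the text explains as "no contact date known alive on Patient Contact/Overall Survival log eCRF page". For these patients the "censoring date will be defined as the latest among the following dates recorded on the eCRF". Most of the 13 bulleted sources are direct observations: laboratory and AFP samples, ECOG, FACT-Hep, Child-Pugh, imaging and TheraSphere administration. The list also holds AE end dates, sorafenib stop dates, Best Available Care end dates, procedure stop dates and, last, "Date of study exit on Study Exit eCRF page". No entry carries a known-alive condition, and the list has no upper limit at the data cut-off.

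Three other places bear on this:

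- Protocol 9.2.20 gives four routes out of the study: death, withdrawal of consent, administrative reasons, and a decision by investigator or sponsor. It adds: "Lost to follow-up is not an adequate reason for withdrawal".
- SAP 6.2.1.3 imputes partial AE and Best Available Care end dates to month end. For an AE end date with day and month both missing, "it will be set to December 31 of the AE end year".
- The only OS sensitivity analysis named in SAP 8.6.1 concerns poolability. SAP 5.2, which lists changes from the protocol's analyses, does not mention the fallback.

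**The concern.** A study-exit date is not by itself evidence that the patient was alive. Someone who drops out of contact without withdrawing consent has no obvious exit route until an administrative or sponsor decision, which could come long after the last observation. The survival contact at the data cut-off helps only if the patient can be reached. Because the rule takes the latest date, a late exit date overrides every real observation on the list.

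Such a patient then stays in the log-rank risk set as a non-death while a death would go unrecorded. That raises the Kaplan-Meier curve. It can move the hazard ratio in either direction, depending on which arm carries more of this time. The primary test and every OS summary would inherit the error, and no planned analysis would reveal it.

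**Working it through.** **1. The plan's own figure.** Inputs from SAP 4.4 and Appendix 5: HR 0.754, looks at 188, 250 and 417 deaths, Z boundaries 2.430, 2.429 and 2.093. At look k the mean of Z is √(d_k/4) × |ln HR|; at the final look √(417/4) × 0.2824 = 2.88. Correlations between looks are √(d_j/d_k). The trivariate normal gives 79.8% power and a one-sided alpha of 0.0250; 419 deaths give 80.0%. The stated 417 deaths and 80% reproduce. They are design inputs and the point does not change them.

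**2. Deaths that could go unseen.** The planned loss allowance is 5% × 520 = 26 patients. Assume, as an upper bound, that all 26 fall into the fallback, 13 per arm, each alive at last contact. With exit g months later and planned medians of 10.7 and 14.2 months:

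expected unseen deaths = 13 × (1 − 0.5^(g/10.7)) + 13 × (1 − 0.5^(g/14.2))

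This gives 1.4, 4.1, 7.5 and 12.8 for g = 1, 3, 6 and 12. At 12 months: 13 × 0.540 + 13 × 0.443 = 12.8.

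**3. Effect on the test.** Simulation with 247 patients per arm (520 × 0.95 / 2), exponential survival, control median 10.7 months, uniform accrual over 60 months and cut-off at month 100 (potential follow-up 40 to 100 months). Loss is uniform over months 0 to 12. Significance means p ≤ 0.0358 in favour of TheraSphere (SAP Table 8, 417 deaths), final look only, with 2,000 to 3,000 trials per row. Each trial was analysed with lost patients censored at true last contact, then at the exit date. All lost patients use the fallback unless stated. The cut-off is a calendar date rather than a death count, so the absolute percentages are indicative; the change is what matters.

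| True HR | Loss, control / TheraSphere | Exit date | Mean HR | Significant |
|---|---|---|---|---|
| 0.754 | 5% / 5% | 6 months after loss | no material change | no material change |
| 0.754 | 5% / 5% | 12 months after loss | 0.754 to 0.756 | 82% to about 82% |
| 0.754 | 5% / 5% | study close | 0.75 to 0.785 | 82% to about 69% |
| 0.754 | 5% / 5%, one in five in fallback | study close | 0.750 to 0.759 | 82% to 79% |
| 0.754 | 8% / 2% | 12 months after loss | 0.75 to about 0.78 | 82% to about 70% |
| 0.754 | 8% / 2% | study close | 0.75 to about 0.89 | 82% to about 20% |
| 1.0 | 5% / 5% | study close | 1.00, unchanged | 1.7% to 1.9% |
| 1.0 | 2% / 8% | 12 months after loss | 1.00 to about 0.97 | 2% to 4–5% |
| 1.0 | 2% / 8% | study close | 1.00 to about 0.88 | 2% to about 21% |
| 1.0 | 2% / 8%, one in five in fallback | study close | — | 2% to about 4% |

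**4. Cross-check under the planned 60 + 18 months.** A separate simulation (1,500 trials per setting, 5% lost per arm, boundary 2.093) applied a fixed gap. With the gap in both arms, the HR is multiplied by 1.000, 1.001, 1.003 and 1.008 for 1, 3, 6 and 12 months at true HR 0.754. With the gap in the TheraSphere arm only, the factors are 0.997, 0.991, 0.983 and 0.968. At true HR 1, a one-arm 12-month gap shifts mean Z by 0.42 towards TheraSphere and raises one-sided rejection from about 1.5% to 4.0%. Kaplan-Meier medians in an affected arm rise by about 0.05 to 0.6 months.

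**The case against.** The strongest reply is that the fallback is narrow. A patient lost after any known-alive entry on the survival log is censored by the main rule, which is sound. Protocol 9.1.2.2 and 9.1.3.5 ask for telephone contact until death when patients stop for progression and cannot attend, Protocol 9.2.20 requires survival follow-up after stopping for intolerance or an AE, and SAP 8.6.1 adds a contact at the data cut-off. Few patients may therefore reach the fallback, and nothing equates them with the 5% allowance. Exit can also be a real encounter: consent withdrawal usually involves a living patient, and Protocol 9.1.4 attaches ECOG, laboratory, imaging and quality-of-life assessments to exit where appropriate. All of this stands. It limits the size but does not supply the missing known-alive condition.

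Three stronger readings are tempting, and the documents do not support them:

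- That lost patients do gain years of survival. No exit lags are given; a gain is possible, not shown.
- That imputed dates enter the list. SAP 6.2.1.3 imputes some of these fields, but the list speaks of dates recorded on the eCRF. This is an ambiguity. Month-end imputation would add at most 30 days; only an AE end date known by year alone could add up to about 12 months.
- That medication end dates in general count. The Prior and Concurrent Medications page is not listed; only Best Available Care and sorafenib dates are.

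**Conclusion.** The point holds as a defect of wording in the primary endpoint. The fallback admits a date with no known-alive condition, against the SAP's main censoring rule and Protocol 10.2.2.1. Followed literally, it could give a wrong censoring time.

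The size is unknown, because neither the number of fallback patients nor the lag to exit is given. On the assumption that the full 5% loss uses the fallback, the effect is negligible with equal loss and lags up to 12 months. It is material only if exit is dated at study close or if loss differs strongly by arm. No document indicates a 2% / 8% split; it is a stress case. A reader might infer that the trial's result is biased, or biased towards TheraSphere. Neither follows: the direction depends on the arm affected, and with equal loss at true HR 1 the false-positive rate barely moves. Should-fix.

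**What to change.** In SAP 8.6.1, change the fallback only:

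- Use the study-exit date only if the eCRF documents contact with the living patient on that date.
- Otherwise censor at the latest complete, non-imputed date of direct patient observation, no later than the data cut-off.
- State that dates imputed under SAP 6.2.1.3 do not enter this derivation.
- Report the number of fallback patients by arm. Adding the lag from last direct observation to exit would show whether the issue matters.

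Leave the survival-log rule and the data cut-off rule for all other patients as they are. A general rewrite to last observed date would override the existing rule that patients confirmed alive around the cut-off are censored at the cut-off.

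The cost is one paragraph of SAP text and a small programming change, largely on data already collected, with a check of what the exit form records about contact. A few patients get slightly shorter follow-up.
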